
AIM 1: Explore and identify, using qualitative methods, acceptable and appropriate app content and features of the *Sense2Quit App* to support smoking cessation and relapse prevention in PLWH who smoke. We will conduct focus groups, design sessions, and usability assessments with HIV-positive daily smokers, former smokers, and usability experts. This feedback will guide tailoring of the app to this population of smokers.

AIM 2: Conduct a pilot randomized controlled trial to examine the feasibility, acceptability, and preliminary efficacy of the *Sense2Quit App*. We will randomize 60 HIV-positive smokers to the *Sense2Quit App* plus the Fossil Gen5E smartwatch, standard smoking cessation counseling, and nicotine replacement therapy (active condition) versus

standard smoking cessation counseling plus referral to NYC Quitline (control) in order to examine group differences in rate of quit attempts, 7-day point prevalence abstinence, and sustained abstinence.

AIM 3: Employ the RE-AIM framework to assess the potential scale-up of the *Sense2Quit App*.

IMPACT: Given the high rates of tobacco use among PLWH, the Sense2Quit App has considerable potential for reducing morbidity and mortality among PLWH who smoke.

AIM 4: Testing with Confounding Gestures. To improve the accuracy of smartwatch smoking detection within the current version of the app, we will perform additional testing on the smartwatch with participants who will complete a set of hand gestures to distinguish them from smoking gestures.

STUDY TIMELINE

We will implement a 2-year timeline to accomplish study specific aims. The details of the study activities, including development of the *Sense2Quit App* and the detailed timeline for the clinical trial, are listed in **Table 1**.

Table 1.

Timing (Year/Month)	Enrollment Target	Milestones
Year 1	“Just in Time” 1-3	
 Protocol & manual of procedures finalized Institutional Review Board (IRB) approvals Recruitment: Pre-screen potential participants, contact participants from database, advertisements/brochures in local clinics, provider meetings, presentations to community groups about study
		
 Aim 1 – Focus Group Sessions Coding of qualitative data begins
		
 Aim 1 – Design Sessions Code and analyze qualitative data

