Inclusion criteria: For Aim 1, (1) PLWH; (2) ≥ 18 years of age; (3) current or former smoker (where smoking is defined as ≥ 5 cigarettes a day for the past 30 days, past smoker is defined as having at one point smoked a minimum of ≥ 5 cigarettes per day for a period of at least 30 days) and (4) understand and read English; Aims 2 and 3 follow the same inclusion criteria with the added criteria that (1) PLWH will be confirmed through medical records or pill bottles for ART medications; (2) only current smokers are eligible (where smoking is defined as ≥ 5 cigarettes a day for the past 30 days); (3) own an Android smartphone (if they do not have a phone compatible with the app, they will be provided with one to use during the study); (4) not pregnant or breastfeeding (due to contraindications for Nicotine Replacement Therapy [NRT]); (5) permanent contact information; (6) interested in quitting smoking within 30 days; and (7) blows ≥ 5 CO into a breath analyzer at baseline. For Aim 4) participants will be PWH who smoke cigarettes and will either be 1) enrolled participants at their 12-week follow-up visit; 2) participants who are initially eligible for the study after completing the screener but do not qualify based on eCO levels; or 3) participants who already finished Aim 2 (and 3, if applicable).

Exclusion criteria. For Aim 1, participants will be excluded if they do not meet the defined inclusion criteria. For Aims 2 and 3, the exclusion criteria will be (1) use tobacco products other than cigarettes (i.e., cigars, piped tobacco, chew, snuff); (2) planning to move within 6 months of enrollment; (3) alcohol dependence measured through the AUDIT-C⁶⁰; (4) positive history of a medical condition that precludes nicotine patch use; (5) current use of NRT or other smoking cessation medications (e.g., Chantix or Zyban); (6) current enrollment in another smoking cessation program; and (7) household member is also participating in the Sense2Quit study (due to study contamination). For Aim 4, participants will be excluded if they fail to meet the inclusion criteria.

Inclusion of Individuals

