The study team under the direction of the MPIs will determine eligibility for inclusion, explain the purpose of the study, answer any questions, and obtain written consent from the participants. Informed consent will be obtained for each of the study components in Aims 1 and 2, and 4. Interested volunteers who agree to participate will sign an electronic consent form. Potential risks and strategies for managing risks will be carefully explained as part of informed consent procedures. The study team will use REDCap's E-Consent Framework to electronically collect and store consent documents. REDCap uses survey features to consent research participants and forms can be completed via computer, mobile phone or tablet. CUMC- approved REDCap is secure with restricted access that ensure confidentiality of a participant's identity, study participation and personal information. Additionally, REDCap is easy to navigate, and information will be on one scrollable page.

There is functionality within the system to stop and continue at a later time. REDCap also allows for generation of a copy of the informed consent form signed by the study participant, which can be downloaded at any time. In REDCap, all versions of the IRB-approved e-Consent Form and all signed e-Consent Forms can be accessed and retrieved easily.

AIM 1. Explore and identify, using qualitative methods, acceptable and appropriate app content and features of the *Sense2Quit App* for smoking cessation and relapse prevention in PLWH who smoke.

Table 2. Overview of Aim 1 Research Design and Methods

	Cycle I: Relevance Cycle	Cycle II: Design Cycle: Develop/Build	Cycle III: Design Cycle: Evaluate
Sample	
 • 40 PLWH who smoke or are former smokers 	
 • 10 PLWH who smoke 	
 • 5 experts in human computer interaction for heuristic evaluation • Usability Testing: 20 PLWH who smoke or are former smokers
Instruments	
 • Focus Group Guide 	
 • Interview guide • Preliminary designs of mobile apps 	
 • Usability Testing Survey • Heuristic Evaluation Survey • Health-ITUES^{61, 62}

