Data Analysis. Mean severity scores will be calculated for each heuristic principle. Evaluators’ comments about usability problems on the evaluation form and the recordings will be used to refine the prototype App.

Usability Testing with End-Users (PLWH).

Participants. We will recruit 20 PLWH who are either current or former smokers and have not participated in the earlier phases of the study activities to evaluate the prototype user interface screens. Eligibility criteria will be the same as described above for Aim 1. We will use similar recruitment methods as those used for the other study aims.

Procedures. Participants will be assigned tasks to perform on all screens of the app and their use of the App will be recorded using an audio recording device. After the usability evaluation, participants will rate the prototype’s usability using the Health Information Technology (IT) Usability Evaluation Scale (Health-ITUES)^{61, 62}. This tool differs from traditional scales as it is designed to support customization at the item level to match the specific task/expectation and health IT system while retaining standardization at the construct level; it has been validated for mHealth technology evaluation⁶³. Compensation: Eligible participants will be able to receive \$40 for participating in the 2-hour usability testing evaluation. Data Analysis. Analysis will be based on recordings of user sessions, transcriptions, notes, and the user survey. The team will search for critical incidents characterized by comments, silence, and repetitive actions. We will review these using the recordings and summarize incidents and written comments. Descriptive statistics of the Health-ITUES will be calculated.

AIM 2: Conduct a pilot randomized clinical trial to examine the feasibility, acceptability, and preliminary efficacy

of the *Sense2Quit App*.

Purpose: The purpose of this aim is to conduct a pilot feasibility study of the preliminary efficacy of the *Sense2Quit App* for improving tobacco cessation in PLWH who smoke.

Study Design: The study will be conducted with 60 PLWH who smoke and will be randomized to two arms. Participants will be randomly assigned to receive the *Sense2Quit App* (active) or a control condition (standard smoking cessation counseling session). Participants will also receive a survey at baseline, 4, and 12 weeks post-baseline.

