Data Analysis: This is a pilot study to assess preliminary feasibility, acceptability, and efficacy. Descriptive statistics will be used for all analyses. The rate of quit attempts will be calculated as the proportion of smokers who attempt to quit (i.e., no smoking during a 24 hours period); 7-day point prevalence abstinence will be calculated as the proportion of smokers who are biochemically verified (saliva cotinine) 7-day abstinence at a given time point; and sustained abstinence will be calculated as proportion of days of no smoking starting on the quit date among those who attempt to quit. We will provide point estimates and corresponding confidence intervals of these measures for each arm. Because of our small sample sizes, we will obtain Clopper-Pearson exact confidence intervals based on the binomial distribution. Given the small sample size, the purpose of the arms is to monitor for unexpected, gross differences between the two groups. To determine acceptability, we will ask participants in both arms how useful each of the intervention components were (1 = *Not at all useful* to 7 = *Extremely useful*) and whether they would recommend the program to a friend (1 = *Definitely would not recommend* to 7 = *Definitely would recommend*). For the intervention to be deemed acceptable, the mean level for each of these measures would have to be five or

higher. The efficacy of the intervention will be based on saliva- confirmed 7-day point prevalence abstinence at the final study visit. Lost-to-follow-up participants will be included as smokers.

NOT-OD-15-102: Consideration of Sex as a Biological Variable: In accordance with NIH guidance, we will include sex as a biological variable in the study design (enroll equal numbers of males and females), analyses, and reporting. We will report all primary and secondary outcomes separately by sex to enhance rigor and transparency of our findings in addition to including sex in all multivariate models.

AIM 3: Employ the RE-AIM framework to assess the potential scale-up of the *Sense2Quit App*.

In addition to testing the Efficacy of the *Sense2Quit App*, we will concurrently measure the four remaining RE-AIM dimensions⁸⁸ as follows:

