Participants who have not yet participated in Aim 2 will complete the baseline survey prior to participating in Aim 4 procedures. All Aim 4 participants will complete the required hand gestures (See table below) as well as smoking gestures for a total of approximately 30 minutes. Study staff will 1) connect the watch with the smartphone; 2) have participant wear the watch on their smoking hand; 3) open the smartphone to start data collection by pressing the start button and assigning the label for the particular activity they are about to perform; 4) repeat each activity listed above in three postures (sitting on a chair, standing, walking around) for a duration of 5 seconds; and 5) stop data collection by pressing the stop button after 5 seconds of the activity being performed. Participants will also complete the optional actions with the opportunity to omit some of them.

	Action	Required?
1	Drinking a beverage without a straw	Yes
2	Drinking beverages with a straw	Yes
3	Eating a meal with a spoon or fork	Yes
4	Eating a snack with a hand	Yes
5	Talking with a hand gesture	Yes
6	Using a phone (making a phone call)	Yes
7	Adjusting glasses	Yes
8	Arm cross	No
9	Brushing teeth	No
10	Gym activity (e.g. lifting, Zumba)	No
11	Scratching face	No
12	Applying lipstick	No
13	Coughing	No
14	Yawning	No
15	Whistling	No
16	Eating a lollipop	No
17	Playing harmonica	No
19	Pinching the chin	No
20	Wiping the nose	No
21	Massaging somewhere on the head	No
22	Waving	No

Compensation:

Participants will receive \$30 in the form of a Bank of America pay card following the completion of the Aim 4 activities.

LIMITATIONS AND ALTERNATIVES

- 1) An important limitation is that we are relying on self-report of NRT use among study participants, and while we will track our administration of NRT to study participants, we are limited in our ability to validate whether participants have used the NRT.
- 2) We carefully considered our control condition and although referring control arm participants to the NYC quitline, which will therefore give them access to an NRT supply may underestimate the effect of the *Sense2Quit* App, we believe that it is imperative to offer NRT/access to NRT to both arms since this is standard of care for persons who are trying to quit smoking.

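### The Aim 2 criteria do not exclude people who took part in Aim 1, so some acceptability raters and some controls may already know the app

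*Combined protocol and SAP*

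**What the plan says.** Under Participants, Aims 2 and 3 take over the Aim 1 inclusion criteria and add others. One addition is that "only current smokers are eligible (where smoking is defined as ≥ 5 cigarettes a day for the past 30 days". Of the seven exclusions, two come near this point. Item 6 is "current enrollment in another smoking cessation program", which concerns other programmes. Item 7 applies if a "household member is also participating in the Sense2Quit study (due to study contamination". Neither concerns the person's own history in Sense2Quit.

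Aim 1 exists to shape the app: "This feedback will guide tailoring of the app to this population of smokers". Table 2 gives its samples: "40 PLWH who smoke or are former smokers" in focus groups, 10 smokers in design sessions, and 20 current or former smokers in usability testing. The section on usability testing with end-users requires people who "have not participated in the earlier phases of the study activities to evaluate the prototype user interface screens" and says that recruitment methods are similar across the aims. Usability participants rate the prototype on Health-ITUES. Table 3 lists the same scale among the Aim 2 follow-up measures.

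Acceptability is decided by a fixed rule on two kinds of 1-to-7 rating, usefulness of each component and willingness to recommend. The Data Analysis section of Aim 2 states: "For the intervention to be deemed acceptable, the mean level for each of these measures would have to be" five or higher. Randomisation is 1:1, stratified only by sex assigned at birth.

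**The concern.** The protocol accepts the principle twice. It wants usability testers who are new to the project, and it treats a housemate's participation as contamination. The randomised trial has no matching rule for someone who personally sketched the interface or worked through the prototype screens.

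Two things are at stake. First, someone who helped to shape or test the app is not a naive rater, and that person's score enters a mean compared with a fixed cut-off. A usability participant allocated to the app would also complete Health-ITUES a second time, on a product revised partly on that participant's own advice. Second, an Aim 1 participant allocated to control would already know content that the control arm is not meant to receive. Table 3 lists no item on earlier Sense2Quit participation, so the overlap would be neither prevented nor measured.

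**Working it through.** No stated figure is in dispute. The 199 per arm for a powered trial (20% against 10%, two-sided 0.05, 80% power) reproduces exactly with the pooled-variance formula and is unaffected by this point.

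**Who could overlap**
- Aim 1 headcount if every group is separate: 40 + 10 + 20 = 70. If all 10 design participants come from the focus groups: 40 + 20 = 60. The 20 usability participants must be new.
- Most exposed: 10 design + 20 usability = 30. The 10 are smokers by definition. How many of the 20 currently smoke is not stated.
- Trial places: 60. Table 1 of the study timeline puts Aim 1 in Year 1 and the start of trial enrolment in month 12.

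**Raters per arm:** 30 at enrolment; 30 × 0.80 = 24 after the 20% attrition given under Sample Size and Power.

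**Effect on the mean**
Let m be the mean among naive raters, f the share of raters with Aim 1 exposure, and b their average difference in points.
- Observed mean = m + f × b.
- Share needed to reach the cut-off: f = (5 − m) / b.

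The documents give none of m, f or b, so all values below are assumptions. Counts are rounded up.

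| m | b | f needed | of 30 | of 24 |
|---|---|---|---|---|
| 4.9 | 1.0 | 0.10 | 3 | 3 |
| 4.8 | 1.5 | 0.13 | 4 | 4 |
| 4.8 | 1.0 | 0.20 | 6 | 5 |
| 4.8 | 0.5 | 0.40 | 12 | 10 |
| 4.5 | 1.0 | 0.50 | 15 | 12 |

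The direction can reverse. With m = 5.2 and b = −1, 7 exposed raters of 30 give 5.2 − 7/30 = 4.97, a fail where naive users would pass.

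**How much overlap that takes.** Under 1:1 allocation, 6 exposed people in one arm correspond to about 12 among the 60 enrolled. That is 12/70 = 17% to 12/60 = 20% of all Aim 1 participants, or 12/30 = 40% of the most exposed. If the acceptability mean were pooled over both arms, the required share f would be the same.

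**The case against.** Much can be said on the other side, and part of it stands.

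- *Reach.* A reader might infer that every Aim 1 current smoker qualifies for Aim 2. The documents do not support that. Aim 2 also requires, among other things, confirmed HIV status, interest in quitting within 30 days and a qualifying breath CO reading, and it excludes other tobacco use, alcohol dependence and current cessation medication. Former smokers drop out altogether. The figure of 60 to 70 is a ceiling on Aim 1, not an estimate of overlap.
- *Depth of exposure.* Focus-group members discuss barriers, triggers and desired content; they do not use the app. Design participants sketch an interface and, according to Table 2, review possible designs. Only the usability group uses the prototype, in one session of about two hours, while it is still changing. This is why the concern concentrates on 30 people.
- *Contamination of controls.* Having seen screens is not receiving the intervention. A control participant has no study watch, no sensor-triggered messages and no study-supplied nicotine replacement. Randomisation balances earlier exposure in expectation. That helps the comparison of arms, but it does not help an acceptability mean judged against an absolute cut-off.
- *Aim 4.* A reader might infer that people who wore the watch in Aim 4 also flow into the trial. Aim 4 draws on participants at the 12-week visit, people who have finished Aim 2, and people who failed the CO criterion, so ordinary flow does not lead into Aim 2. The gesture session is about 30 minutes of labelled movements and, as described, shows no messages or quit content. The phrase "Participants who have not yet participated in Aim 2 will complete the baseline survey prior to participating in Aim 4 procedures" leaves re-screening unaddressed, but one word does not establish a pathway.
- *Purpose.* Both sample-size sections give estimation of cessation rates as the pilot's goal, so acceptability is one stated aim among several, and all analyses are descriptive.

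**Conclusion.** The gap is real. As written, people who took part in Aim 1 and meet the other criteria can be randomised in Aim 2, contrary to the logic that the protocol applies to usability testing and to household members. The consequence is a possible shift in the acceptability decision and some prior knowledge of the app among controls. Neither can be sized from the documents. Under the central assumption (naive mean 4.8, exposed raters 1 point higher), 6 of 30 raters or 5 of 24 settle the decision; over the assumed values in the table the count runs from 3 to 15 of 30. Upward bias is plausible but should not be stated as fact, because co-designers may be harsher critics. The documents do not support extending the point to Aim 4, or claiming that the cessation comparison is biased. This is a modest weakness in a descriptive pilot, worth correcting because correction is cheap.

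**What to change.** Add an exclusion, applied at Aim 2 enrolment, for prior participation in a Sense2Quit focus group, design session or usability test. Add one item to the phone screener and check the answer against the list linking participants to study ID numbers, which the privacy and data security plan already provides for.

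If enrolment has already begun, record prior Aim 1 participation for everyone enrolled, report it by arm, and repeat the acceptability means without those participants.

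Do not make Aim 4 participation an Aim 3 exclusion. Enrolled participants may do the gesture session at their 12-week visit, and such a rule would bar app-arm participants from any later Aim 3 interview.

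The cost is one criterion, one screener item and a recruitment pool smaller by at most about 70 people, fewer in practice because former smokers are ineligible anyway. The clinic alone cares for more than 2,300 people (a figure that includes children and adolescents), and recruitment also runs through community organisations and online. The sample stays at 60, 30 per group.

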Sample Size and Power: The goal of this pilot study is to estimate the cessation rates in each arm to obtain an effect size for future larger studies. To conduct a hypothesis test for the comparison of cessation rates between the two intervention arms will require a minimum 199 people in each arm (total sample=398) for at least 80% power. This calculation was based on a 2-sided test with the type I error of 0.05, and assuming a 20% cessation rate in the *Sense2Quit App* group (intervention) and a 10% cessation rate in the control arm. The 10% difference would be equivalent to a medium effect size (Cohen's $d=0.45$). In this pilot study, we propose a total sample of 60 (30 per group) of whom we expect there to be 20% attrition. Therefore, this study is not powered to detect a significant difference between study arms. Instead, for the sample size (30 per group), this study will have at least 80% probability that the standard error of the cessation rate estimates $\leq 7\%$. We assume that the expected cessation rates range from 10% to 20%, and therefore the sample size is sufficient to provide a power estimation for a larger trial with acceptable reliability.

Recruitment and Retention: Strategies for recruitment and retention are described in the Recruitment and Retention attachment. We will enroll 60 PLWH who smoke tobacco. Inclusion/exclusion criteria are described above.

Screening: Potential study participants will provide verbal informed consent by phone or complete an eConsent form through REDCap prior to completing a phone screening process that assesses eligibility. If eligible, participants will attend a baseline session described below.

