Procedures: Eligible participants will attend a baseline visit at Columbia University School of Nursing. On the day of their baseline appointment, study participants will meet a study staff member who is trained by a nurse. The study staff member will run the baseline appointment. Upon arrival, participants will be asked to blow into a breath analyzer to complete assessment of their study eligibility. Breath samples will be analyzed for exhaled carbon monoxide (CO) levels (in ppm) using a breathalyzer (MicroTM basic Smokerlyzer[®]). After providing written consent, participants will complete a baseline questionnaire (See **Table 3**). They will be asked complete a timeline to follow back to track their cigarette use for the previous 30 days and to complete the Fagerstrom Test for Nicotine Dependence. Survey instruments will be collected through Qualtrics at baseline, and 4 weeks, and 12 weeks after baseline.

Following completion of baseline study instruments, participants will be randomized (1:1) to the App arm or the control arm, stratified by sex assigned at birth. Participants in both arms will undergo a smoking cessation counseling session. Notes from the counseling session will be recorded on RedCap. Participants will receive an informational packet during the counseling session which will consist of: 1) an appointment reminder sheet, nicotine patch information, nicotine gum information, nicotine lozenge information and smoking substitution ideas (Intervention) or 2) a reminder sheet, NYS Quitline information, and smoking substitution ideas (control). Participants in the control arm will be referred to the New York State Smoker's Quitline. Through the Quitline, participants in the control arm can receive NRT if desired and receive additional smoking cessation counseling. A study staff member will follow up to see how many participants called, texted and/or visited the Quitline webpage. Participants in the intervention arm (App arm) will be provided with combination NRT. Participants will be given an 8-week supply of combination NRT and will be instructed to begin using their NRT supply directly after their baseline visit.

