Possible AEs that are unanticipated will be brought to the attention of the Coordinators and reported immediately to both site IRBs. All study staff will be trained to recognize and report AEs and SAEs. Possible AEs will immediately (within 24 hours) be brought to the attention of the Lead at each site by study staff who identify the event. The Site Lead will report the AEs and SAEs to the IRB in writing as soon as possible, but within 7 calendar days for death or life-threatening events and within 15 calendar days for all other AEs or SAEs. The IRBs will determine whether it is appropriate to stop the study protocol temporarily or will provide suggestions/modifications to the study procedures as necessary. Possible modifications include adding these possible adverse events to the consent form and re-consenting all study participants. The PIs will be responsible for monitoring participant safety on a monthly basis at regularly scheduled research meetings. They will keep a written log of all events and ensure that the IRB is contacted immediately. They will also keep a log of the outcome of IRB decisions regarding AEs and apprise the research team of any changes that need to occur because of IRB decisions.

STATISTICAL DESIGN AND POWER

Sample Size and Power. The goal of this pilot study is to estimate the smoking cessation rates in each arm to obtain an effect size for future larger studies. To conduct a hypothesis test for the comparison of cessation rates between the two intervention arms, it requires a minimal sample size of 199 per group (total 398) for at least 80% power. This calculation was based on a 2-sided test with the type I error of 0.05, and assuming a 20% cessation rate in the *Sense2Quit* App group (intervention) and a 10% cessation rate in the control arm. The 10% difference would be equivalent to a medium effect size (Cohen's $d=0.45$). In this pilot study, we propose a total sample of 60 (30 per group). Therefore, this study is not powered to detect a significant difference between arms. Instead, we estimated the minimal sample size for the estimation of cessation rates in each arm with acceptable reliability. For the sample size (30 per group), this study will have at least 80% probability that the standard error of the cessation rate estimates $\leq 7\%$, assuming expected cessation rates ranging from 10% to 20%. Therefore, the sample size is sufficient to provide estimation with acceptable reliability.

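### With 30 per arm, the stated precision (at least 80% probability that the SE is at most 7%) fails above a cessation rate of about 13%, and is 43% at the active arm's planned 20%

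*Combined protocol and SAP*

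**What the plan says.** The sample size argument appears twice, under Aim 2 (Sample Size and Power) and again under Statistical Design and Power. Both state that the pilot is not powered for a comparison and that its purpose is to estimate the cessation rate in each arm "to obtain an effect size for future larger studies". Both then support 30 per arm with a precision statement: "this study will have at least 80% probability that the standard error of the cessation rate estimates" does not exceed 7%. The Statistical Design section ties this to rates of 10% to 20% in the same sentence; the Aim 2 section gives the range in the next one. The ends of that range are the plan's own planning rates, 10% for control and 20% for the Sense2Quit arm.

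The conclusions differ slightly. Aim 2 says that "the sample size is sufficient to provide a power estimation for a larger trial with acceptable reliability". The Statistical Design section says that "we estimated the minimal sample size for the estimation of cessation rates in each arm with acceptable reliability".

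On the analysis, Aim 2 (Data Analysis) and Statistical Design and Data Analysis both say: "We will provide point estimates and corresponding confidence intervals of these measures for each arm", using Clopper-Pearson limits. Both also say: "Lost-to-follow-up participants will be included as smokers".

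**The concern.** At a true rate of 20% with 30 participants, the theoretical standard error is already 7.3%. An estimate centred above the 7% limit is unlikely to fall at or below it 80% of the time, so the claim looks unattainable at the upper end of its own range, which is where the active arm is expected to lie.

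The plan gives no other quantitative reason for 30 per arm, and its statement that the pilot can inform the power of a larger trial rests on this one. If the figure is wrong, those planning the larger trial would take the pilot's precision as better than it is.

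A related gap concerns the output. The declared product is an effect size, but intervals are planned only within each arm, so the difference that would size the next trial has no planned measure of uncertainty.

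**Working it through.** **Inputs.** From Aim 2, Sample Size and Power: "we propose a total sample of 60 (30 per group) of whom we expect there to be 20% attrition"; rates of 10% (control) and 20% (active); limit 7%; probability at least 80%. From Aim 2, Procedures: allocation is 1:1. Because losses count as smokers, the denominator stays at 30. The plan does not name its standard error formula; the usual one is assumed here and alternatives are tried below.

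**The companion figure.** The 199 per arm for a future test does reproduce. With pooled rate 0.15:

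(1.960·√(2·0.15·0.85) + 0.842·√(0.20·0.80 + 0.10·0.90))² / 0.10² = 198.96, rounded up to 199.

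The problem is therefore confined to the precision statement.

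**Which outcomes meet the limit.** SE(x) = √[(x/30)(1 − x/30)/30]:

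| Quitters x of 30 | SE |
|---|---|
| 5 | 6.80% |
| 6 | 7.30% |
| 7 | 7.72% |
| 8 | 8.07% |

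So an SE of at most 7% means x ≤ 5. (x ≥ 25 also qualifies but adds a negligible amount.)

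**Probability of meeting a limit**, with X binomial (30, p):

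| True rate p | P(SE ≤ 7%) = P(X ≤ 5) | P(SE ≤ 8.1%) = P(X ≤ 8) |
|---|---|---|
| 10% | 92.7% | 99.8% |
| 15% | 71.1% | 97.2% |
| 20% | 42.8% | 87.1% |

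P(X ≤ 5) equals 80% at p = 13.3%, so the claim fails over roughly the upper two thirds of the range: (20 − 13.3)/(20 − 10) = 0.67.

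**Alternative readings at p = 20%:**

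- n − 1 in the denominator: 42.8%
- Agresti-Coull SE: 42.8%
- SE rounded to a whole percent (x ≤ 6): 60.7%
- Clopper-Pearson half-width divided by 1.96: 25.5%
- Normal approximation: 39–41%
- 24 completers (20% attrition removed from the denominator): 26.4%, with 78.6% at p = 10%
- Attrition assumed to lower the active-arm rate to 16%, with n = 30: 65.5%

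Averaging the probability over 10–20% gives 69.9%. None reaches 80%.

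**Smallest n per arm meeting the plan's criterion throughout 10–20%.** The lowest probability over the range, found at p = 20%, is 78.4% at n = 38, 85.9% at n = 39 and 83.9% at n = 40, and it stays above 80% for the larger sizes checked (41 to 59). The minimum is 39.

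**The bound that 30 per arm supports.** At p = 20%, P(X ≤ 7) = 76.1% and P(X ≤ 8) = 87.1%. Eight quitters must therefore be allowed, which gives SE ≤ 8.07%, stated as 8.1%. A bound of 8.0% would reach only 76.1%.

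**The between-arm difference.** At the planning rates, 6/30 against 3/30 gives +10 percentage points, Newcombe 95% CI −8.8 to +28.5.

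**The case against.** The arithmetic is hard to contest; its importance can be. At a true rate of 20% the expected count is 6 of 30, exactly where the standard error steps from 6.8% to 7.3%. The probability drops sharply because of that step, while the standard error overshoots by only 0.3 points, and its mean at 20% is 7.1%. If 7% is read as rounding to 7%, the claim holds at 15% (84.7%) and up to about 16%. No test or stopping rule uses the figure. The per-arm exact intervals will show the uncertainty plainly: about 7.7% to 38.6% for 6/30 and 2.1% to 26.5% for 3/30. Finally, the missing difference interval is a separate matter, and the plan deliberately limits the between-arm comparison to watching for gross, unexpected differences.

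Most of this stands as an argument about size. The shortfall in the standard error is small, and the difference interval neither follows from the error nor makes it worse. What does not stand is any rescue of the claim: even the rounded reading gives 60.7% at the active arm's planned rate. As for the interval, two separate ones do not directly give the uncertainty of a difference, and an effect size is the pilot's stated product.

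**Conclusion.** The precision statement is wrong as written, in both places. With 30 per arm the probability is 93% at the control planning rate but 43% at the active planning rate, against a claimed minimum of 80%. The description of 30 as an estimated minimum also fails, since the stated criterion first holds across the range at 39.

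The result rests on a binomial model, the usual standard error formula and a denominator of 30; the conclusion is unchanged under every variant tried. The consequence is moderate: no inference or decision rule is affected and 30 per arm need not change, but the sole numerical justification for the sample size should be correct. The between-arm interval is a sensible accompanying addition, not part of the error.

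**What to change.** 1. In both Sample Size and Power sections, state that 30 per arm gives at least 80% probability that the standard error is at most 8.1% for cessation rates of 10–20%. Word this as the precision the chosen sample provides. The figure is derived from n = 30 and does not by itself show that the precision is adequate.
2. Under Statistical Design and Power, remove the statement that 30 was the estimated minimal sample size.
3. Under Aim 2, remove or soften the conclusion that the sample suffices for a power estimation.
4. In Aim 2 (Data Analysis) and in Statistical Design and Data Analysis, add the between-arm risk difference in biochemically verified 7-day abstinence with a 95% confidence interval, for example Newcombe's, reported descriptively beside the per-arm Clopper-Pearson intervals.

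The cost is a few words in the two sample size sections and one descriptive line in the analysis. The stated bound loosens from 7% to 8.1%. No participants and no hypothesis test are added.
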